### 4. ANALYSIS VARIABLES

#### 4.1 Demographic and Baseline Characteristics

The following demographic and Baseline characteristics variables will be summarized:

- Following continuous demographic variables and baseline characteristics will be summarized descriptively:
  - Age
  - Height
  - Baseline weight
  - Baseline body mass index (BMI)
  - Duration of AA
  - Duration of current AA episode

- Baseline SALT score
- Baseline Investigator's Assessment of a Target Scalp Lesion (IATS)
- Baseline investigator's global assessment (eyebrows [IGA-EB], eyelashes [IGA-EL], fingernails [IGA-FN])
- Baseline patient's global impression of severity (overall AA [PGIS-AA], AA on scalp [PGIS-S], eyebrows [PGIS-EB], eyelashes [PGIS-EL], fingernails [PGIS-FN])
- Baseline alopecia areata patient priority outcome (AAPPO)
- Baseline hospital anxiety and depression scale (HADS)
- Baseline Eosinophil
- Following categorical demographic variables and baseline characteristics will be summarized with numbers and percentages.
  - Gender
  - Ethnicity
  - Race
  - Participants with AT or AU
  - Participants with baseline SALT: 50 - <75, 75 - <95, and 95 – 100,
  - Participants with atopic disease history/comorbidities
  - Participants with autoimmune history/comorbidities
  - Participants with elevated IgE (>ULN) at baseline
  - Participants with eyebrow, eyelash and fingernail involvement
  - Participants who are JAK-I experienced

Duration of AA (Years): (Date of enrolment – Diagnosis date of AA)/365.25.

Duration of current AA episode (Years): (Date of enrolment – Current episode start date)/365.25.

In cases where only a partial date is available for AA diagnosis or current episode start date, the imputation process will involve substituting "01" if only the day is absent, or "01 Jan" if both the day and month are missing, prior to the calculation of the duration.

## 4.2 Medical History and Alopecia Disease History

Medical history will be coded according to the latest available version (26.0 or higher) of Medical Dictionary for Regulatory Activities (MedDRA). Information on conditions related to AA includes diagnosis of AA, AA history, scalp AA subtype etc.

## 4.3 Prior and Concomitant Medications/Procedures

Medications/Procedures (excluding non-drug) will be recorded from the day of informed consent until the end of extended follow-up period. Medications will be coded with anatomical therapeutic chemical (ATC) levels, according to the latest available version (WHO Drug B3 Global, Sep 2022 or higher) of World Health Organization Drug Dictionary (WHODrug).

Prior medications/procedures: Medications taken or procedures performed prior to the first dose of Investigational Medicinal Product (IMP). All the medications that are stopped prior to the first administration of the study drug are considered under this category.

**Concomitant medications/procedures:** medications taken or procedures performed following the first dose of study drug through the end of extended follow-up period. i.e., procedures or medication with end date on or after the first administration of the study drug irrespective of the start date, or ongoing during the study period.

**Prohibited medications and non-drug therapies:**

Treatment with the following concomitant medication is prohibited:

- Use of topical treatments for AA within 2 weeks before the Baseline (Day 1) visit and until completion of the follow-up (including the extended follow-up) period, such as corticosteroids, calcineurin inhibitors, JAK inhibitors (e.g., ruxolitinib), antimicrobials, anthralin, DPCP, squaric acid, minoxidil or any other medication which, in the opinion of the investigator, may affect hair regrowth;

*Note: Topical treatments are permitted outside of the scalp, eyebrows and eyelashes.*

- Use of non-biologic systemic (oral or injectable) agents including conventional immunosuppressants or immunomodulators (e.g., corticosteroids, methotrexate, MMF, cyclosporine A, azathioprine, hydroxychloroquine, sulfasalazine and other approved drugs with potential immunosuppressive effects, within 4 weeks or 5 half-lives, whichever is longer, prior to the Baseline (Day 1) visit and until completion of the follow-up (including the extended follow-up) period;
- Use of oral JAK inhibitors within 8 weeks prior to the Baseline (Day 1) visit and until completion of the follow-up (including the extended follow-up) period;
- Use of oral or injectable agents (minoxidil, apremilast, finasteride, hydroxymethylglutaryl coenzyme A (HMG-CoA) reductase inhibitors [statins], herbal medicines) for the treatment of AA within 4 weeks prior to the Baseline (Day 1) visit and until completion of the follow-up (including the extended follow-up) period;

*Note that the listed medications are permitted if they are not indicated for the treatment of AA **AND** have been used at a stable dose until the completion of the study. These medications are prohibited if they are indicated for the treatment of AA **OR** if they have been newly initiated or had their dose modified during the study.*

- Use of any biologic therapy (e.g., mAbs against IL-17, IL-4, and IL-13 or other investigational products) or platelet-rich plasma within 3 months or 5 half-lives, whichever is longer, prior to the Baseline (Day 1) visit and until completion of the follow-up (including the extended follow-up) period;
- Use of phototherapy for the treatment of AA within 4 weeks before the Baseline (Day 1) visit and until completion of the follow-up (including the extended follow-up) period, such as ultraviolet (UV) A or UVB, or any other type of light therapy that, in the opinion of the investigator, may affect hair regrowth.
- Receipt of a live vaccine, including live attenuated, within 2 months before the Baseline (Day 1) visit and until 3 months after the last administration.

- Other medications or non-drug therapies, in the opinion of the investigator, that could affect AA from screening to study completion.

## 4.4 Prior and concomitant non-drug therapies and procedures

Non-drug therapies will be recorded from the day of informed consent until the end of extended follow-up period and each therapy will be coded according to the latest available version (26.0 or higher) of MedDRA.

## 4.5 Efficacy Variables

Since the primary objective of the study is to assess the safety arising from multiple doses of IMG-007, the analysis of efficacy will be conducted as secondary and exploratory.

### 4.5.1 Secondary Efficacy Variable

The secondary efficacy endpoint is the percentage change in SALT from baseline to Week 24.

#### Severity of Alopecia Tool

SALT is a quantitative assessment of AA severity by the investigator based on scalp terminal hair loss. The investigator utilizes a visual aid showing the division of the scalp hair in four quadrants, with the top constituting 40%, the back 24%, and the right and left side of the scalp of 18% each of the total surface (Olsen et al 2004). A composite score is derived based on the percentage of terminal hair loss in each of the four scalp views (areas). The SALT score will range from 0 to 100.

### 4.5.2 Exploratory Efficacy Variables

#### 4.5.2.1 Key Exploratory Endpoints

The key exploratory endpoints are:

- Absolute and percentage changes from baseline in SALT by visit
- Proportion (%) of participants achieving a 30% improvement in SALT score (SALT30) by visit

Investigator's Assessment of a Target Scalp Lesion

A target scalp lesion that best represents the overall severity (50% or greater hair loss) of AA, in the upper parietal region of scalp, if feasible, will be selected at the Baseline (Day 1) visit. The same target scalp lesion will be assessed at all subsequent visits.

At the scheduled clinic visits, the investigator will rate the severity of target scalp lesion as it looks on the day of study visit on a 5-point scale ranging from 0 = “no” to 4 = “very severe”. The investigator’s assessment of a target scalp lesion (IATS) will be performed by the investigator.

#### Investigator’s Global Assessment (Eyebrows, Eyelashes, and Fingernails)

At the scheduled clinical visits, the investigator will rate the severity of eyebrow hair loss (IGA-EB), eyelashes hair loss (IGA-EL), and fingernail changes (IGA-FN) as it looks on the day of study visit on a 5-point scale ranging from 0 = “no” to 4 = “very severe”.

The investigator’s global assessment will be performed by the investigator.

#### Patient’s Global Impression of Severity of Alopecia Areata

At scheduled clinic visits, participants will be asked to rate patient’s global impression of severity (PGIS) of their overall AA (PGIS-AA) and AA on the scalp (PGIS-S), eyebrows (PGIS-EB), eyelashes (PGIS-EL), and fingernails changes (PGIS-FN) using a 5-point scale ranging from 0 = “none” to 4 = “very severe”.

#### Patient’s Global Impression of Change of Alopecia Areata

At scheduled clinic visits, participants will be asked to rate patient’s global impression of change (PGIC) in AA (PGIC-AA) and AA on scalp (PGIC-S), eyebrows (PGIC-EB), eyelashes (PGIC-EL), and fingernails (PGIC-FN) using a 5-point scale ranging from 1 = “much better” to 5 = “much worse”. Participants will be asked to provide this rating in comparison to just before they started taking study treatment.

#### Alopecia Areata Patient Priority Outcomes

The alopecia areata patient priority outcome (AAPPO) scale is a participant self-administered 11-item questionnaire that measures hair loss (4 items using a 5-point scale), emotional symptoms (4 items using a 5-point scale), and activity limitations (3 items using a 5-point scale) over the past week ([Wyrwich et al 2022](#)).

The AAPPO is completed by the participant in the study clinic.

#### Hospital Anxiety and Depression Scale

The hospital anxiety and depression scale (HADS) is a 14-item self-assessment scale that determines the levels of anxiety (7 items) and depression (7 items) that a patient is experiencing over the past week. The HADS utilizes a 4-point Likert response scale (e.g., 0 to 3) for each item. Scores for each domain (anxiety and depression) can range from 0 to 21, with higher scores indicating greater anxiety or depression ([Zigmond et al 1983](#)).

The HADS is completed by the participant in the study clinic.

## 4.6 Safety Variables

### 4.6.1 Adverse Events and Serious Adverse Events Variables

Adverse events and serious adverse events will be collected from the time of informed consent signature until the end of the study. All adverse events will be coded according to the latest available version (26.0 or higher) of MedDRA.

An **Adverse Event** is the development of any untoward medical occurrence in a participant or clinical study participant who is administered with a medicinal product that does not necessarily have a causal relationship with this treatment. An AE can therefore be any unfavorable and unintended sign, symptom, or disease temporally associated with the use of a medicinal product, whether or not considered related to the medicinal product, including the following conditions:

- 1) Any newly occurred undesirable medical condition (including newly diagnosed disease or signs and symptoms when a diagnosis is pending);
- 2) Exacerbation of a chronic or intermittent pre-existing condition including either an increase in frequency and/or intensity of the condition. However, events that are unequivocally due to natural disease progression of the underlying disease being studied should not be reported as an AE during the study unless judged by the investigator to be more severe than expected for the participant condition;
- 3) Clinically significant laboratory abnormality.

A **Serious Adverse Event** is defined as any untoward medical occurrence that, at any dose, meets one or more of the criteria listed:

- **Results in death**
- **Is immediately life threatening**
- **Requires in-patient hospitalization or prolongation of existing hospitalization**
- **Results in persistent or significant disability or incapacity**
- **Is a congenital abnormality or birth defect**
- **Is an important medical event** (i.e., that may jeopardize the participant or may require medical treatment to prevent one of the outcomes listed above.)

Details for each criterion above are presented in the study protocol section 8.1.2.

**Non-treatment emergent AEs** are AEs that are developed or worsened in severity compared to the baseline during the period between participant enrolment and the first study drug administration. All AEs collected during the screening period are considered as non-TEAEs.

**Treatment-emergent AEs (TEAEs)** are AEs that developed or worsened in severity compared to the baseline during the treatment and follow-up period (including the extended follow-up). As only the worsening pre-existing AEs and new AEs reported during the treatment and follow-up period (including the extended follow-up) will be collected in the study, all AEs collected

during the treatment and follow-up period (including the extended follow-up) are considered as TEAEs.

**TEAE that are infusion related reaction** will be summarized. Localized injection/infusion reactions that may include pruritus, pain, erythema, swelling, rashes, or bleeding around the injection/infusion site. Systemic injection/infusion-related reactions may be immediate type or delayed type immune complex-associated hypersensitivity reactions (e.g., serum sickness).

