3 STUDY OBJECTIVES AND ENDPOINTS

Study objectives and endpoints are summarized in [Table 3](#).

Table 3 Study Objectives and Endpoints

Primary Objective	Primary Endpoint
To evaluate AEs emergent from multiple doses of IMG-007 in adult participants with AA	Incidence of TEAEs
Secondary Objectives	Secondary Endpoints
To evaluate the efficacy of multiple doses of IMG-007 in AA participants as measured by SALT at Week 24	Percentage change in SALT from baseline to Week 24
Exploratory Objectives	Exploratory Endpoints
To further evaluate the efficacy of multiple doses of IMG-007 in AA participants as measured by SALT and other investigator's assessments and patient reported outcomes	
• Absolute and percentage changes from baseline in SALT by visit• Proportion (%) of participants achieving a 30% improvement in SALT score (SALT30) by visit 

Abbreviations: AA = alopecia areata; AAPPO = Alopecia areata patient priority outcomes; ADA = anti-drug antibody; AE = adverse event; CL = central compartment clearance; EB = eyebrows; ECG = electrocardiogram; EL = eyelashes; FN = fingernails; HADS = Hospital anxiety and depression scale; IATS = Investigator's assessment of a target scalp lesion; IGA = Investigator's global assessment; PD = pharmacodynamic; PGIC = patient global impression of change; PGIS = patient global impression of severity; PK = pharmacokinetic; S = scalp; SALT = Severity of Alopecia Tool; TEAE = treatment-emergent adverse event; Vc = central compartment volume

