8.1.3 Adverse Event Variables

The following variables will be collected for each AE:

- AE (verbatim)
- The date when the AE started and stopped
- The maximum severity reported or changes in severity (report only the maximum severity for a calendar day). See [Section 8.1.4](#) for severity assessment.
- Whether the AE is serious or not
- Investigator causality rating against the study treatment (yes or no). See [Section 8.1.5](#) for causality assessment.
- Action taken with regard to study treatment
- Administration of treatment for the AE
- Outcome

In addition, the following variables will be collected for SAEs, either on the eCRF or SAE reporting form:

- Date the AE meeting the criteria for SAE (SAE onset date)
- Date the investigator becoming aware of the SAE
- Seriousness criteria
- Date of hospitalization
- Date of discharge
- Probable cause of death

- Date of death
- Whether an autopsy was performed
- Causality assessment in relation to study procedure(s)
- Causality assessment in relation to other medication
- Description of the SAE

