11.3 Statistical Analysis

11.3.1 Analysis of Safety

Safety variables including incidence, severity, and changes from baseline of relevant parameters (such as vital signs, ECGs, and clinical laboratory values) will be summarized.

- AEs will be coded using the Medical Dictionary for Regulatory Activities (MedDRA, the version currently in use by the Sponsor at the time of database lock). TEAEs are defined as events started after the initiation of the first dose of study treatment or events present that worsen after the start of dosing. The number and proportion of participants experiencing one or more TEAEs will be summarized by severity, and relationship to study treatment.
- Prior and concomitant medications will be coded using the World Health Organization Drug Dictionary. The number and proportion of participants taking prior and/or concomitant medications will be summarized.
- Vital signs (systolic and diastolic blood pressure, pulse, respiratory rate, and temperature) and ECG parameters will be summarized by visit descriptively. Changes from baseline, number, and proportion of participants with clinically important values will be presented descriptively.
- Clinical laboratory parameters, including changes from baseline, where appropriate, will be summarized using descriptive statistics, by post-dosing shift from baseline in the normal or abnormal category of laboratory values by visit, and number and proportion of participants with a treatment-emergent clinically significant abnormal value based on predefined criteria, and data listings.

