### **Screening Period:** Day -35 to Day -1 (up to 5 weeks)

After providing informed consent, participants will be assessed for compliance with protocol requirements and study eligibility. Only in exceptional circumstances, when information concerning eligibility is outstanding (e.g., delayed laboratory results), will a longer screening period be permitted for up to three business days. Upon consultation with the medical monitor, a participant may be rescreened one time. Circumstances that may permit rescreening include, but are not limited to, a laboratory test result that does not meet eligibility requirements.

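### The SAP counts an adverse event that starts on Day 1 before the first infusion as treatment-emergent; the protocol, and the SAP's own non-TEAE definition, do not

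*SAP*

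**What the plan says.** The primary endpoint is "Incidence of TEAEs" (Protocol 3). Protocol 11.3.1 defines TEAEs as "events started after the initiation of the first dose of study treatment or events present that worsen after the start of dosing".

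SAP 4.6.1 gives two rules for each class:

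- **Non-TEAEs.** The opening sentence covers AEs that develop or worsen "during the period between participant enrolment and the first study drug administration". The next sentence is a shortcut for one period: "All AEs collected during the screening period are considered as non-TEAEs".
- **TEAEs.** The opening sentence requires an AE that is new or worse relative to baseline. A shortcut follows, on the ground that only new or worsening AEs will be collected in that period: all AEs collected "during the treatment and follow-up period (including the extended follow-up) are considered as TEAEs".

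In SAP 2.3, screening ends on Day -1 and the treatment period starts on Day 1 (Baseline), not at the start of the infusion. SAP 5.8.1 builds the 24-week and 36-week TEAE tables from events whose start date lies between the date of first administration and the relevant visit. Protocol 8.1.3 lists the AE timing variable as "The date when the AE started and stopped", with no mention of a clock time.

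**The concern.** Day 1 contains an interval before the drug is given. Blood draws, vital signs and other baseline procedures take place in it, and AEs are already being collected. An event starting then (from a needle or line placement, for example) cannot be treatment-emergent in the protocol's sense. The SAP's shortcut makes it one, and the date-level filter in SAP 5.8.1 does not take it out again.

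The endpoint affected is the primary one. Two programmers working from the protocol and from the SAP could produce different numerators, and SAP 4.6.1 alone supports either class for the same event. SAP 1 says that methodological deviations from the protocol are documented, but the readable text documents none on this point. Cohort 1 has only six participants and preferred-term rows have small counts, so one misplaced event is visible there.

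**Working it through.** The documents give no figure for this point, so the check compares definitions first and then scales the effect.

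**1. Is there a pre-infusion interval on Day 1?** Yes. AEs are collected from signature of consent (Protocol 8.2.1). On dosing days the infusion follows the other assessments (Protocol Table 1, footnote 9; Protocol 7.1.3), and pre-dose PK and ADA samples are drawn in the hour before dosing (footnotes 15 and 16).

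**2. How is each kind of event classed?**

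| Onset | Protocol 11.3.1 | SAP 4.6.1, TEAE shortcut | SAP 4.6.1, opening non-TEAE sentence | SAP 5.8.1 date filter |
|---|---|---|---|---|
| Known date before Day 1, not worsened, reported later | not TEAE | arguably TEAE | non-TEAE | removed |
| Day 1, before the infusion | not TEAE | TEAE | non-TEAE | kept |
| Day 1, after the infusion starts | TEAE | TEAE | not covered | kept |

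Only the middle row is in conflict after the date filter. The screening-period shortcut for non-TEAEs does not settle it, because screening ends on Day -1. Two other SAP rules do not help. The partial-date rules (Appendix 11.2) leave complete dates alone, and the visit windows (Appendix 11.3) place the whole of Day 1 in Baseline without splitting it at the infusion.

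**3. Effect of one participant.** If the pre-infusion event is that participant's only counted event, incidence rises by 1/n:

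- Cohort 1: 1/6 = 16.7 points
- Cohort 2: 1/24 = 4.2 points
- Pooled: 1/30 = 3.3 points

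**4. Expected effect.** Let q be the share of participants with a pre-infusion Day 1 AE and p the share with at least one true TEAE. If the two are independent, the expected rise in the proportion with any TEAE is q × (1 − p).

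- p = 34/44 = 77.3%, from the blinded single-dose data in healthy participants, active and placebo together (Protocol 2.2). It is used only for scale.
- q is not in the documents. I assume 2% to 10%.
- q = 2%: 0.02 × 0.227 = 0.0045, about 0.5 points.
- q = 10%: 0.10 × 0.227 = 0.0227, about 2.3 points.
- With p from 50% to 90%, the range runs from 0.02 × 0.10 = 0.2 points to 0.10 × 0.50 = 5.0 points.

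**5. Chance that it matters at all.**

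- At least one such event among 30 participants: 1 − (1 − q)^30 = 45% (q = 2%) to 96% (q = 10%).
- At least one participant changes the pooled count of any TEAE, with p = 77.3%: 1 − (1 − 0.227q)^30 = 13% to 50%.
- The same for Cohort 1: 1 − (1 − 0.227q)^6 = 3% to 13%.

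**The case against.** The strongest reply is that the shortcut was never meant to catch pre-dose events. It follows a sentence that requires change from baseline, and SAP 6.1 sets baseline as the last valid measurement before dosing. Read that way, the SAP agrees with the protocol. This does not hold up, because a new AE on Day 1 before the infusion satisfies the shortcut's literal terms, and nothing later excludes it.

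Other parts of the reply stand, and they rule out stronger readings that a reader might infer:

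- **Late-reported screening events inflate the count.** They do not if the onset date is known: the start-date filter in SAP 5.8.1 removes them from both sets of TEAE tables.
- **The same event will appear in both tables.** The SAP does not plan this. If only the two shortcut sentences are applied, a Day 1 event lands in the TEAE table alone. The overlap is an ambiguity between sentences.
- **The data cannot separate the cases.** This would be an inference from the protocol's variable list. The eCRF is not among the documents and may hold an onset time or a flag.
- **Harmless events are blamed on the drug.** TEAE is a timing class. Causality is assessed for each AE (Protocol 8.1.5), and related TEAEs are tabulated separately.
- **A safety signal could be hidden.** The error runs the other way and overstates incidence.

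The extension to Week 36 is not a fault either, because the protocol collects AEs through the extended follow-up.

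**Conclusion.** The point holds for one group of events: onset on Day 1 before the first infusion. The SAP counts them towards the primary endpoint, contrary to the protocol and to its own opening definition of non-TEAEs. This is a stated rule that misclassifies events, so it is more than missing detail.

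The expected size is small: about 0.5 to 2.3 points on pooled incidence. That rests on the assumed 2% to 10% frequency, on independence, and on a background rate borrowed from a different population and a single dose. It should not be read as a typical shift of 16.7, 4.2 or 3.3 points, which applies only to a participant with no other TEAE in the reporting window. Cohort 1 and preferred-term rows are the most exposed. A correction before database lock is worthwhile because the endpoint is primary and the change is cheap.

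**What to change.** In SAP 4.6.1 and 5.8.1, define a TEAE as the protocol does: onset, or worsening of an existing event, after the start of the first infusion. Delete the sentence that makes every AE collected from Day 1 onward a TEAE, and state that TEAE and non-TEAE are mutually exclusive.

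For onsets dated Day 1, use the onset time or a before/after-infusion flag if the eCRF has one; otherwise query the site. Count unknown timing as a TEAE, which matches the SAP's conservative handling of missing relatedness (6.2) and partial start dates (Appendix 11.2). If neither eCRF nor source can settle the timing, this default reproduces the present result, so the gain is limited to events that can be resolved.

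The cost is SAP wording and one data query before lock.
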